#### 7.4 *Pharmacological Intervention*

The pharmacological intervention will be the instillation of the ophthalmic solution in the bottom of the conjunctival sac during the waking period, in any of the following study groups:

1. Preservative free PRO-087 ophthalmic solution. Dropper bottle. Multidose  
1 drop every 4 hours for 90 days.
2. Systane® Ultra ophthalmic solution. Dropper bottle. Multidose.  
1 drop every 4 hours for 90 days.
3. Systane ® Ultra preservative free ophthalmic solution. Single-use vials.  
1 drop every 4 hours for 90 days.

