## 6. Summary

---

Drug product ID	PRO-087
Study drug:	0.1% sodium hyaluronate, free-preservative 0.18% chondroitin sulphate
Therapeutic indication:	Ocular surface lubricant
Protocol ID:	SOPH087-0415/IV
Sponsor:	Laboratorios Sophia, S.A. de C.V.
Version:	2
Date:	February 2016
Study title	Efficacy and Safety of the Ophthalmic Solution PRO-087 versus Systane ® Ultra and Systane ® Ultra Preservative Free on the Tear Film Dysfunction Syndrome from Mild to Moderate  Clinical trial

Main objective	To evaluate the effectiveness of preservative-free ophthalmic formulation PRO-087 (by Laboratorios Sophia, S.A. de C.V.) to restore the anatomical and physiological characteristics of the ocular surface, as well as its distribution and the characteristics of the mild to moderate tear film dysfunction syndrome compared to Systane ® Ultra and Ultra Systane ® preservative free (by Laboratorios Alcon, S.A. de C.V.).
Study design	Controlled, randomized, double-blind, masked clinical study, comparing the safety and efficacy of preservative-free PRO-087 vs Systane Ultra with preservative and Systane Ultra preservative free, in subjects with mild to moderate tear film dysfunction syndrome, for a period of 90 days plus 15 days of remote surveillance, in which one of the three agents will be administered (PRO-087, Systane® Ultra or Systane® Ultra preservative free) with a q.i.d. dosage. in both eyes, with regular follow-up visits (5 overall).
Variables to evaluate	
Best-corrected visual acuity
 
Intraocular pressure
 
Ocular surface
 
Anterior segment examination
 
Posterior segment examination
 
Tear film break-up time
 
Schirmer test
 
Corneal depithelization
 
Goblet cells count
 
Adverse events

Groups	Subjects with a clinical diagnosis of mild to moderate tear film dysfunction syndrome between 18 and 90 years old, without concomitant eye diseases nor requiring different treatments of any of the three interventions in this study They will be randomized in 3 groups where PRO-087, Systane® Ultra o Systane® Ultra preservative free will be administered.

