8.2 Drug Product of Study

The formulation PRO-087 is made of the following active agents: 1.80 mg/ml of chondroitin sulphate and 1.00 mg/ml of sodium hyaluronate, as well as the inactive agents: boric acid, decahydrate sodium borate, polysorbate 80, sorbitol, sodium chloride, dihydrate disodic edate, potassium chloride, hexahydrate magnesium chloride, purified water.

It is dispensed in a dropper bottle (which has a container closure system that allows to preserve the solution) for a multidose administration, as a preservative free ophthalmic solution of 10ml.

**Systane® Ultra** is made of the following active agents: 0.4% of polyethylene glycol 400 and 0.3% of propylene glycol, and the inactive agents: aminomethyl propanol, boric acid, hydroxypropyl guar, 0.001% of POLYQUAD® (polyquaternium-1) with conservative, potassium chloride, purified water, sodium chloride, sorbitol, hydrochloric acid/sodium hydroxide to adjust pH. It is dispensed in a dropper bottle for multidose administration, as ophthalmic solution of 10 ml.

**Systane® Ultra preservative free** is made of the following active agents: 0.4% of polyethylene glycol 400 and 0.3% of propylene glycol, and the inactive agents: aminomethyl propanol, boric acid, hydroxypropyl guar, potassium chloride, purified water, sodium chloride, sorbitol, hydrochloric acid/sodium hydroxide to adjust pH. It is dispensed as ophthalmic solution in single-use vials of 0.4 ml. Pharmacological intervention dosage with drug products of study: 1 drop 4 times daily for 90 days.

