### *17.6 Treatment compliance*

The study drug administration compliance from the patients will be assessed in the Laboratorios Sophia facilities once the dropper bottles of each patient are returned by the investigator; each bottle will be weighed in an analytical balance and the difference will be obtained regarding the initial weight of the container, all values over 80% will be considered as appropriate compliance to the treatment.

In case the study drug compliance is less than 80%, the obtained results will be considered to be analyzed via the intention to treat, see statistical analysis section.

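### The regimen is worded as one drop every 4 hours while awake in section 7.4 but as four times daily in sections 6 and 8.2, a gap of 0 to 25% in expected use that bears on the 80% adherence rule

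*Combined protocol and SAP*

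**What the plan says.** Section 7.4 (Pharmacological Intervention) lists the three arms and repeats the same line for each: "1 drop every 4 hours for 90 days". Its lead sentence limits instillation to the hours awake: "in the bottom of the conjunctival sac during the waking period".

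Section 6 (Summary, study design row) describes administration "with a q.i.d. dosage. in both eyes". Section 8.2 (Drug Product of Study) closes its description of the products with "Pharmacological intervention dosage with drug products of study: 1 drop 4 times daily for 90 days".

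Section 17.6 (Treatment compliance) has returned dropper bottles weighed: "the difference will be obtained regarding the initial weight of the container, all values over 80% will be considered as appropriate compliance to the treatment". Results from subjects below 80% are to be analysed by intention to treat. The efficacy criterion in section 14.1 is conditioned on adherence of 80%. The tolerability and safety criteria that follow in section 14 are conditioned on adherence of at least 80%.

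**The concern.** One wording is an interval, so the daily count depends on how long the subject is awake. The other is a fixed daily count. They can describe the same behaviour, but not for every subject, and no section says which one governs.

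Two things are at stake. The first is exposure: subjects with long waking days would use more product under the interval wording. The second is classification. An adherence percentage needs an expected amount, and if that amount depends on which section is read, the same actual use can fall on either side of 80%. That line enters the criteria by which the product is to be called effective, tolerable and safe, and it also determines how results are handled.

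**Working it through.** The plan states no expected number of drops and no expected weight, so there is no figure of its own to reproduce. The check is a direct dose count.

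**Inputs from the documents**
- Interval wording: one drop every 4 hours while awake, 90 days (section 7.4).
- Fixed wording: 4 times daily (sections 6 and 8.2), 90 days (section 8.2).
- Both eyes (section 6).
- Adherence line: 80% (sections 14 and 17.6).

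**Assumptions, not in the documents**
- Waking period W of 12 to 18 hours.
- First drop on waking.

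**Drops per eye per day under the interval wording:** floor(W/4) + 1.
- W = 12: 3 + 1 = 4.
- W = 14: 3 + 1 = 4.
- W = 16: 4 + 1 = 5.
- W = 18: 4 + 1 = 5.

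The count is therefore 4 for 12 to under 16 hours and 5 for 16 to under 20 hours. The change at 16 hours lies inside the assumed range.

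**Total drops, both eyes, 90 days**

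| Drops per eye per day | Total | 80% of total |
|---|---|---|
| 4 | 4 × 2 × 90 = 720 | 576 |
| 5 | 5 × 2 × 90 = 900 | 720 |

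The ratio is 900/720 = 1.25, so expected use differs by 0% for shorter waking days and by 25% for longer ones.

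**Effect on the adherence percentage for a subject following the four-times-daily wording**
- All doses taken: 720/720 = 100% against one expectation and 720/900 = 80.0% against the other.
- 90% of doses taken: 0.90 × 720 = 648 drops. Then 648/720 = 90% and 648/900 = 72%.

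Against 900, full use sits exactly on the line and any missed drop puts the subject below it. Against 720, the subject can miss 720 − 576 = 144 drops before falling below 80%.

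**In the other direction:** a subject told to use 5 per day who takes 576 of 900 drops (64%) would score 576/720 = 80% against the four-times-daily expectation.

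**The measure itself:** section 17.6 works from container weight, not drops. It gives no expected weight or volume under either wording, so these drop percentages only show how far the two wordings can move the result. Section 17.6 also speaks only of dropper bottles, whereas section 7.4 lists single-use vials for the third arm and section 8.2 gives their size as 0.4 ml.

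**The case against.** The strongest reply is that the two wordings are one regimen written twice. Section 7.4 confines dosing to waking hours, and for a waking day under 16 hours the interval gives exactly four drops. The same line applies to all three arms, so the discrepancy does not by itself favour any of them. Subjects below 80% are not discarded but analysed by intention to treat. No sample size or power figure depends on dosing frequency. All of this stands, and it limits the size of the point. It does not make the wordings interchangeable, because they part at 16 hours awake and nothing in the plan settles the matter.

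A reader might infer several stronger things that the documents do not support:
- **Round-the-clock dosing, six drops a day.** The waking limit in section 7.4 excludes this. With a first drop on waking, a sixth drop needs at least 20 hours awake.
- **Undefined exposure.** Under the stated assumptions it is ambiguous by 0 to 25%.
- **Full four-times-daily use fails the section 14 criteria.** At exactly 80.0% it meets both forms of the condition there. It misses only the stricter form in section 17.6, where adequate compliance must exceed 80%. The real difficulty is the lack of margin.
- **The conflict in wording causes the missing denominator.** Section 17.6 would lack an expected weight even if all three sections agreed.
- **Subjects are given no clear instruction.** Consent pages were removed from the text available for review, so missing subject instructions cannot be held against the plan.

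**Conclusion.** The point holds as an internal inconsistency in the plan, not as a criticism of a design choice. Section 7.4 conflicts with sections 6 and 8.2 for any subject awake 16 hours or more: 5 drops per eye per day against 4, or 900 against 720 over the trial. For subjects awake 12 to under 16 hours the wordings coincide.

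The consequence is for classification. A subject taking 90% of four-times-daily doses scores 90% or 72%, depending on which wording sets the expectation, and so changes sides of the 80% line used in sections 14 and 17.6. The missing expected consumption and the omission of vials in section 17.6 are a separate gap that a single agreed regimen would not close.

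The size rests on an assumed waking period and on the first drop being taken on waking. How many subjects are awake for 16 hours or more cannot be known from the documents. The correction should be made. Which regimen is intended is for the sponsor to settle, and no view on that is offered here.

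**What to change.** Reconcile sections 6, 7.4 and 8.2 so that one regimen statement appears in all three, with the sponsor deciding which is intended, and check that the subject instructions match.

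In section 17.6, state the expected consumption over 90 days under that regimen from which the 80% is taken. Give it in weight or volume, because the measure is a weight difference. Give it for each container type, and say how use of the single-use vials will be measured.

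The cost is a text correction to the protocol and any matching subject materials. It changes neither the sample size nor the visit schedule.

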#### 7.5 *Allocation to intervention groups*

The allocation to the study groups will be held in the visit outlined in the study schedule, randomly, through a specialized software that uses random number tables to achieve a uniform allocation in each intervention group.

#### 7.6 *Ethic considerations*

This protocol conforms to the Good Clinical Practices (GCP) and principles from the 18th Medical Assembly in Helsinki, Finland in 1964 and the amendments made in Tokyo, Japan 1975, Venice, Italy 1983, Hong Kong 1989 and the 48th General Assembly Somerset West, South Africa in 1996, 59th General Assembly, Seoul, Korea, 2008, 64th General Assembly, Fortaleza, Brazil, 2013, where medical research (clinical research) is contemplated.

Also, according to the specifications of the General Law of Health of Mexico, on research for health, section 17, this study is considered on the subsection III with greater risk to the minimum, by the cell sampling and drug administration. Under this legal framework, the full respect for the person, life and safety is maintained.

### **Research Ethics Committee**

The principal investigator will submit the study protocol, informed consent, investigator handbook, materials to deliver to the patient, recruiting materials, and the necessary documents, in accordance with local requirements, to a Research Ethics Committee, supported by the National Bioethics Commission, and with current registration in the Federal Commission for Protection against Sanitary Risks (COFEPRIS).

The study will not start in the investigation center without first obtaining the approval of the Research Ethics Committees and Research Committee concerned, having met the local regulatory requirements, having obtained the signature of confidentiality agreements, economic proposal and the contract signature of each of the senior research physicians.

Information for the subject and informed consent form:

The consent form must be obtained before the patient is treated with any procedure specified in the protocol.

The written consent documents must incorporate the elements of informed consent described in the Declaration of Helsinki and the ICH Guide to Good Clinical Practice and will be in compliance with all applicable laws and regulations.

The principal investigator (or a member of the research medical team of the site properly specified by the principal investigator in the form of delegation of responsibilities) will provide the prospective participant with all the information relating to the characteristics of the study, its potential risks, benefits, objectives and procedures thereof. This information shall be in a language understandable to the subject, it will be explained to the patient that he/she is entitled to discontinue the participation in the study at any stage, without affecting the relationship with the investigator and/or its future assistance. Informed consent will be placed before the potential participant; he/she must have enough time to analyze each and every one of the abovementioned aspects, and, if in doubt, this will be clarified by the person responsible for obtaining the informed consent. Once the participant agrees to participate in the study, he/she must sign and date the written informed consent in the presence of two witnesses, who may or not have relation with the subject of study, who will be involved during the informed consent process and will sign endorsing that the process is carried out prior to any study procedures, which clearly explained the study information and clarified any doubts, if available.

Should a patient be illiterate, the acceptance will be with the fingerprint, and if the patient is unable to grant a proper written informed consent, a patient representative "legally authorized" can provide such consent in name of the subject, in accordance with the laws and regulations.

*The principal investigator must also sign and date this consent.*

Informed consent should be signed in duplicate by all the involved and two witnesses; a copy will be filed in the investigator's folder and another investigator will grant the other copy to the participant.

The investigator must document in the patient clinical chart the date on which the informed consent was signed.

At the time that informed consent is obtained, a unique subject identification number will be assigned, this will be used throughout the study to identify the participant.

### **Amendment to the "informed consent"**

Any changes made to the "informed consent" constitute an amendment to this document and must be submitted for approval before the Research Ethics Committees, and if applicable, before the competent authorities.

In the amendment, a copy of the new version in the official language or languages of the country will be included.

Such amendments could be implemented only after having obtained the written approval of the Research Ethics Committee and having met with the local regulatory requirements, except for an amendment that is required to remove an immediate hazard to the patients in the study.

Each patient affected by the amendment must complete, date and sign two original copies of the new version. The patient will be given a signed original amendment and the principal investigator shall retain the second one.

### **Pregnancy test**

Urine pregnancy test will be taken in the same facilities of the research organization, where the study participant will be provided with a home pregnancy test device, which she will use in private, explaining that she must pour urine on absorbent end of it for 10 seconds; after this she should put the already included plastic cover and let the device stand for 3 minutes on a flat surface with result windows turning up, it is important not to move it during this period.

The result can be seen after 3 minutes and before 15 minutes of conduction. A line is observed in the control window to know that it is working properly, then a pink line will appear in the output window, the intensity may vary, but if present, it is an indicator of a possible pregnancy.

### **Center Organization**

Any person to whom the principal investigator delegates, under its responsibility, part of the follow-up study (co-investigator, sub-investigator, nurse) and any other person involved in the study of this center (cardiologist, pharmacist, etc.) will be included in the format of Delegation of Responsibilities.

This document must be delivered at the start of the study and updated in case one of the people involved in the study at the center is changed.

7.7 Study Plan

## 8. Drug Product of Study

### 8.1 Codes, labelling and storing

The dropper bottles will be delivered on its primary and secondary packaging to the different participating research centers; they will come identified with the ID protocol, below the specification of solution or suspension and content in milliliters, among other data, as illustrated below.

#### 8.1.1 Primary Packaging

Sample:

PRO 087	PRECAUTION: STUDY DRUG FOR INVESTIGATIONAL USE ONLY	Patient No.:	Initials: _____	Study drug No.:	Batch:	Exp.:
Ophthalmic Solution						
Content: 5 ml						

8.1.2 Secondary Packaging

Drug product No.:  Batch:  Expiration date:	PRO-087 Protocol: SOPH087-0415/IV Subject No.: _____ Subject initials: _____ Investigator: _____  Ophthalmic. Apply according to the protocol indication.	REMOVE LABEL  PRO-087 Protocol: SOPH087-0415/IV Drug product No. _____
	Keep at room temperature at no more than 30 °C  Clinical investigation sample  Investigational drug product	PRO-087 Protocol: SOPH087-0415/IV Drug product No. _____

8.2 Drug Product of Study

The formulation PRO-087 is made of the following active agents: 1.80 mg/ml of chondroitin sulphate and 1.00 mg/ml of sodium hyaluronate, as well as the inactive agents: boric acid, decahydrate sodium borate, polysorbate 80, sorbitol, sodium chloride, dihydrate disodic edate, potassium chloride, hexahydrate magnesium chloride, purified water.

It is dispensed in a dropper bottle (which has a container closure system that allows to preserve the solution) for a multidose administration, as a preservative free ophthalmic solution of 10ml.

**Systane® Ultra** is made of the following active agents: 0.4% of polyethylene glycol 400 and 0.3% of propylene glycol, and the inactive agents: aminomethyl propanol, boric acid, hydroxypropyl guar, 0.001% of POLYQUAD® (polyquaternium-1) with conservative, potassium chloride, purified water, sodium chloride, sorbitol, hydrochloric acid/sodium hydroxide to adjust pH. It is dispensed in a dropper bottle for multidose administration, as ophthalmic solution of 10 ml.

**Systane® Ultra preservative free** is made of the following active agents: 0.4% of polyethylene glycol 400 and 0.3% of propylene glycol, and the inactive agents: aminomethyl propanol, boric acid, hydroxypropyl guar, potassium chloride, purified water, sodium chloride, sorbitol, hydrochloric acid/sodium hydroxide to adjust pH. It is dispensed as ophthalmic solution in single-use vials of 0.4 ml. Pharmacological intervention dosage with drug products of study: 1 drop 4 times daily for 90 days.

### *8.3 Handling of the Drug Product of Study*

The drugs will be shipped from the storage center (located in Laboratorios Sophia S.A. de C.V.) previously weighed and packaged.

**The handling of the drug product of study will be the responsibility of the principal investigator in charge of the research center, including:**

- Receipt and storage of drug product of study. The receipt of the drug product of study must be acknowledged by signing and sending back the corresponding format. The drug product of study should be stored in a secure area with restricted access. Some special storage conditions are requested, such as to keep at room temperature of no more than 30° Celsius, for which the doctor will be provided, on loan during the study, with a thermos-hygrometer that records humidity and temperature. Principal investigator or pharmacist assigned must conduct a thermo-hygrometer reading at least once a day, keeping a record of:
  - Current temperature
  - Minimum temperature
  - Maximum temperature
  - Relative humidity
- Data review registered in the of thermo-hygrometer diary will be performed on the clinical monitor during monitoring visits and, in turn, the previously assigned responsible will perform a reading a day directly from the recorder screen, which will have to write down on the corresponding format.
- Expiration date will appear on each box and label.
- The investigator and/or pharmacist of the research center shall use the treatment delivered only for participating subjects of study.
- Drug product of study count:

The investigator and/or pharmacist of the Research Center and/or a person designated by the study team must fill in real time all the documents that the sponsor provides for the management of the drug product of study.

The study monitor will periodically check the handling and counting of the drug product of study.

At the end of the study, the principal investigator and the study monitor will complete a final inventory of drugs, and will record in the appropriate form.

The study monitor will collect the remaining drug product of study for storage and subsequent destruction, after quantifying the remaining amount in each container.

They must report all faults or damages of the drug product of study or of its packaging to monitor the study. The principal investigator shall notify the monitor all complaints received from a subject.

In case of early return of the drug product of study to the sponsor (removal of the batch), the sponsor will prepare an informative letter to the principal investigator and/or pharmaceutical of the research center. This letter will be sent by people locally responsible of the study to each of the study centers. Upon receiving the letter, the investigator and/or pharmacist will identify the subjects who have a treatment at the time the incident is known, and will contact them immediately. The monitor will organize the return of the drug product of study for the purposes of destruction.

